#### Weeks 2, 6

RT-CGM education and use will be coupled to one initial nutrition and exercise counseling session at Week 2 by the diabetes educator. Individually administered nutrition and exercise counseling will be based on a condensed version of the standard 12-session Diabetes Prevention Program Group Lifestyle Balance (DPP GLB, Appendix B) material and received by all participants. All those enrolled in the CGM intervention (N=30) will participate in 2 cycles of RT-CGM with direct feedback on CGM patterns at the second session, Week 2.

Both groups will then follow up and be given diet and exercise education handouts and instruction based on the DPP GLB core nutrtion and physical activity materials (Appendix B) at Week 2. The diabetes and prediabetes CGM intervention groups will also receive additional education on how food and exercise affects bloods sugar, and how to evaluate and respond to their blood sugar changes with RT-CGM (Appendix A). The CGM intervention participants will then wear the RT-CGM device for 10 days at week 2 and at 6 weeks. At week 2, CGM patterns will be reviewed with diet and food logs, and CGM intervention patients will be challenged "to beat their averages. The control group will review their diet and exercise log with the instructor and attempt to continue to make small changes in diet and exercise. Vital signs will be taken at each visit, including waist circumference. Pedometer data will be collected at weeks 6 and 14. Week 2 education on nutrition and RT-CGM will take 1 hour 30 minutes to 2 hours. Week 6 CGM review and measurements will take 1 hour. They will mail their sensors back from the continuous glucose monitoring device after 10 days, along with physical activity and food logs. They continue wearing their pedometers during this time.

Page 8 of 14

#### Week 14

All groups will wear blinded CGM for 10 days, starting at the 14 week visit, and their pedometers. Lipids and hemoglobin A1c will be obtained. Hemoglobin A1c will again be checked through fingerprick in the clinic, and also through serum to LabCorp. Approximately 1 teaspoon of blood will be drawn at that time also. Vital signs will be collected, including height, weight, blood pressure, waist circumference, and resting heart rate. Body composition will also be assessed by bioelectrical impedance using a Tanita scale. Participants will be given other self-report questionnaires on their perception of CGM, physical activity, and wellness. Food and physical activity logs will be reviewed. The intervention group will complete questionnaires on their perception of CGM. Week 14 data collection will take 1 hour 30 minutes. Participants will mail back their pedometers, the sensors from their continuous glucose monitoring device after 10 days, and physical activity and food logs.

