# **RESEARCH PLAN**

### A. Specific Aims

**Hypothesis:** We hypothesize that two sessions of 10 days of RT-CGM in the setting of nutrition and physical activity counseling coupled with education on how exercise and nutrition affect blood sugar levels will promote weight loss in participants with prediabetes and diabetes and reduce glycemic variability.

**Aim 1**: Examine the effect of two 10-day sessions of RT-CGM over 6 weeks on weight loss, change in body composition, activity level and nutritional changes in subjects with diabetes and prediabetes 12 weeks later.

Aim 2: Evaluate participants' perception of RT-CGM as a weight loss tool.

**Aim 3**: Evaluate the effect of RT-CGM on glycemic variability in subjects with prediabetes and diabetes.

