There are a multitude of reasons for the significance and innovation of this protocol. Without weight loss, 15-30% of people with prediabetes may develop Type 2 diabetes within five years(1). In patients with diabetes, as little as 5% weight loss may significantly improve glycemic control (30). It has been hypothesized in previous studies that RT-CGM causes behavior modification in both Type 1 and 2 diabetes but few if any studies have objectively demonstrated how RT-CGM causes behavior modification or its use as a weight loss tool. Because of its simplicity, RT-CGM could be used in community/primary care clinics where other more intensive and complex interventions for weight loss may not be available. It could also be used in the adolescent population with new onset Type 2 diabetes as a teaching tool for both the adolescent and family unit. This would be the first study that would evaluate RT-CGM as a behavior modification and weight loss tool in patients with either prediabetes or diabetes. The DPP educational materials have not been evaluated outside of the core 12 weekly in-person intervention sessions which are time-consuming and costly. This study would provide evidence that a modified DPP approach was effective when combined with RT-CGM. Previous RT-CGM studies in Type 1 and Type 2 diabetes have not used standardized educational lifestyle materials with CGM teaching, which could help create a practice model to use in primary care/community clinics.

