### C. Preliminary Studies

Many studies have demonstrated that RT-CGM can be used in adults and children with both Type 1 and Type 2 diabetes resulting in improvement in HbA1c and/or a reduced frequency of hypoglycemia (17-19). Table 2 shows the average blood sugars of normal, prediabetic, and diabetic patients (24). Our initial research showed that the use of RT-CGM serially over 3 months improved HbA1c by an average of 1.0% in subjects with Type 2 diabetes on no prandial insulin (20). Nutrition and activity changes were not measured but the 3-month HbA1c improvement was sustained for another 9 months without further RT-CGM intervention (21). We hypothesized that the RT-CGM data motivated the subjects to make salutary changes in their diet and exercise habits leading to this long-term improvement in HgA1c (20, 21). However, there has been little direct examination of RT-CGM as a behavior modification/weight loss tool, as most studies have focused on HbA1c changes. Yoo et al. did show that intermittent use (3 days of RT- CGM every month for 12 weeks) produced a significant decrease in calorie

Page 2 of 14

consumption, increase in physical activity, improvement of weight, and a 1% decrease in HbA1c in poorly controlled patients with Type 2 diabetes (22). Allen et al. found that the data from a single three-day session of blinded CGM when combined with subsequent counseling and review of the CGM glucose data with the patient resulted in an increase in physical activity and a decrease in HbA1c by 1.2% and BMI by 0.5 kg/m^2 (23). The only study using RT-CGM in patients with prediabetes showed significant glycemic variability at baseline but did not show decreased glycemic variability or improvement in weight after 6 months, and diet and activity levels were not measured (24, 25). The reasons for the failure to achieve weight reduction in that study may have been due to the lack of specific lifestyle counseling and/or instructions on use/interpretation of RT-CGM to the subjects. In addition, the rigorous RT-CGM schedule in the protocol (6 days of RT-CGM wear on 4 occasions over 3 months) may have been too intense for patients with prediabetes who are generally not even required to perform fingerstick blood glucose measurements.

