### **D.** Research Design and Methods

The central premise of this intervention is that for RT-CGM to be effective as a behavior modification tool for weight loss in patients with prediabetes and diabetes it must include education on interpreting RT-CGM data in the context of appropriate initial lifestyle and weight reduction counseling. We are guided by Social Cognitive Theory, which specifies goal setting as an important strategy (26, 27). This approach has been widely used for understanding and researching behavior change. When specifically applied to nutrition education interventions it has been shown to be successful when the interventions are behaviorally focused and theory driven. Cullen et al. developed a goal-setting process, based on previous work to help dietitians use goal-setting strategies in nutrition counseling by: (1) recognizing a need for change; (2) establishing a goal; (3) adopting a goal-directed activity and self-monitoring; and 4) selfrewarding goal attainment (28, 29). We will follow a counseling protocol that was designed to change efficacy beliefs about diet and activity and follow this basic strategy. In the first session we will: (1) outline benefits of nutrition and activity as based on the DPP and discussed CGM patterns with each participant, i.e. the effect of food and activity on blood sugars; (2) set specific activity and calorie goals, and; (3) monitor with CGM. In the second session, we review and evaluate the CGM patterns and challenge the participants to improve their dysglycemic pattern (goal attainment). We have selected ten days' duration of RT-CGM over two sessions based on the limited previous studies and we anticipate this study will provide important insights on whether or not RT-CGM is effective as a behavior modification tool for weight loss in patients with prediabetes and diabetes.

A maximum number of 45 participants will be recruited that meet inclusion/exclusion criteria for the study. Recruitment information about the study will be made available to all medical personnel including medical assistants, nursing staff, and primary care providers at the

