https://www.diabetesprevention.pitt.edu/index.php/for-the-public/for-health-providers/grouplifestyle-balance-curriculum. In this study, we will offer an adapted brief-intervention DPP in the first meeting. Our intent in providing this material is to support a primarily *self-directed* diet, activity and weight behavior modification context for use of the RT-CGM. Our diabetes educator will be responsible for reviewing the DPP materials and fat, calorie and activity goals at their original session along with materials developed about what different foods and activity does to your blood sugars prior to the initial use of RT-CGM. We reviewed the educational materials and handouts from the 12 sessions and consolidated them into a 12 page handout which was also reviewed by the current director of The Diabetes Prevention Support Center/DPP Lifestyle Resource Core at the University of Pittsburgh. Consistent with social cognitive theory, all participants are given fat and calorie goals based on their initial weight upon enrollment and an

Page 9 of 14

activity goal of 150 minutes of activity weekly with ongoing goal to 300 minutes weekly. They are asked to self–monitor weight, food intake and physical activity levels with goal of 7% weight loss (32).

**Measurements (Appendix C)**: We will measure HbA1c at the beginning of the study period and at 14 weeks. At each visit, blood pressure, weight, height, and waist circumference will be measured. At baseline and 14 weeks, questionnaires on diet and physical activity and selfperception questionnaires will be obtained. In the intervention group at 14 weeks, a questionnaire about CGM technology and perception of benefit of CGM use will be obtained, for diabetics and for prediabetics. Body composition will also be assessed serially by bioelectrical impedance using a Tanita scale at baseline and 6 weeks and 14 weeks. Pedometer data will be downloaded at 2 weeks, 6 weeks and 14 weeks. Physical fitness testing by resting heart rate and three minute stair step (amount of/change in steps climbed in 3 minutes) will also be obtained at baseline and 14 weeks.

**Anthropometrics: Height** will be recorded in centimeters and inches by a Stadiometer. **Weight** will be recorded in pounds and kilograms using a SECA Digital scale. **Waist circumference** will be meaured using a flexible measuring tape, and **blood pressure** taken with an Omron Professional Digital blood pressure machine.

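### A difference between arms would show the effect of a package (RT-CGM, glucose education, pattern review and a glucose challenge), not of RT-CGM alone as Aims 1 and 3 are worded

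*Protocol*

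**What the plan says.** **What the aims claim.** Aim 1 is to "Examine the effect of two 10-day sessions of RT-CGM over 6 weeks on weight loss" and related outcomes. Aim 3 likewise names the effect of RT-CGM on glycemic variability. The hypothesis in the same section is broader: it places RT-CGM within counselling and couples it with education on exercise, nutrition and blood sugar. Section D's central premise also makes education in interpreting RT-CGM a necessary part of the intervention.

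**What the arms receive.** The Weeks 2, 6 text gives both arms the condensed DPP material. It then adds, for one arm, "The diabetes and prediabetes CGM intervention groups will also receive additional education on how food and exercise affects bloods sugar", together with instruction on evaluating and responding to RT-CGM readings, feedback on CGM patterns and a challenge to improve on their averages. Controls go through their diet and exercise log with the instructor and "attempt to continue to make small changes in diet and exercise".

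**Who gets the glucose teaching.** Section D describes a first session in which the team "discussed CGM patterns with each participant, i.e. the effect of food and activity on blood sugars". Study Procedures has the educator review the DPP goals "along with materials developed about what different foods and activity does to your blood sugars prior to the initial use of RT-CGM", without naming an arm.

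**What is common.** Study Procedures gives all participants fat, calorie and activity goals and asks them to monitor weight, food intake and "physical activity levels with goal of 7% weight loss".

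**The concern.** An aim that names RT-CGM invites the conclusion that seeing one's own glucose in real time caused the change. If the CGM arm does better, the food-and-glucose lesson, the educator's review of the CGM trace or the challenge could have contributed, and this design has no contrast that separates them. The protocol itself treats education as active. Preliminary Studies suggests that an earlier prediabetes study of RT-CGM may have failed to reduce weight partly because it lacked counselling and/or instruction, and proposes that more education will help.

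The mismatch over who receives the glucose discussion adds to this. Until the control condition has a single description, a reader cannot say which components the arm difference contains.

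**Working it through.** No figure in the plan rests on this point, so the check is a comparison of passages.

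**1. Components by arm**

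| Component | CGM arm | Control | Source |
|---|---|---|---|
| Condensed DPP counselling and handouts | yes | yes | Weeks 2, 6 |
| Fat, calorie, activity and 7% weight goals | yes | yes | Study Procedures |
| Logs, pedometer, blinded CGM at weeks 0 and 14 | yes | yes | Screening visit; Week 14; Study Procedures |
| Log review with staff | yes, with CGM patterns | yes | Weeks 2, 6 |
| Real-time display and training to read it (R) | yes | no | Weeks 2, 6 |
| Food/exercise-and-glucose education (E) | yes | no; Section D reads as yes | Weeks 2, 6; Section D |
| CGM pattern review (P) | yes | no | Weeks 2, 6 |
| Challenge on glucose averages (C) | yes | no | Weeks 2, 6 |

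**2. What the arm difference estimates.** Let B be everything common to both arms, and take effects as additive for simplicity.

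- Weeks 2, 6 text governs: (B + R + E + P + C) − B = R + E + P + C.
- Controls also get the food-and-activity discussion, as Section D can be read: (B + R + E + P + C) − (B + E) = R + P + C.

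In both cases one number is estimated for several terms, so R is not identified.

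**3. Is the pattern review separable from real-time viewing?** At the week 2 visit the only CGM data are from the blinded wear begun at week 0, because RT-CGM starts at week 2. Controls wore the same blinded sensor, so their patterns exist but are not reviewed with them. As written, the week 2 review is therefore distinct from the display. The week 6 review can draw on real-time data.

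**4. Does sample size help?** Planned allocation is 30 (15 + 15) versus 15 (7 + 8), which agrees with the 22 + 23 = 45 in the Confidentiality section. With a common outcome SD (not given) and two-sided alpha 0.05 (assumed):

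- SE = SD × √(1/30 + 1/15) = 0.316 SD
- 95% half-width = t(43 df) × 0.316 = 2.017 × 0.316 = 0.64 SD
- Difference detectable at 80% power = (1.960 + 0.842) × 0.316 = 0.89 SD

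These describe how precisely the sum is estimated. A larger sample narrows the interval around the same sum.

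**5. What the SAP would estimate.** The SAP plans N=30 (15 prediabetes, 15 diabetes), mentions no control group and takes the time main effect as the relevant effect size. In the notation above that is B + R + E + P + C, with 95% half-width t(29 df)/√30 = 2.045/5.477 = 0.37 SD of change. It absorbs the DPP counselling as well and compares no arms.

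**6. Can the non-display share be sized?** Preliminary Studies reports HbA1c −1.2% and BMI −0.5 kg/m² after "a single three-day session of blinded CGM when combined with subsequent counseling and review of the CGM glucose data with the patient". The sponsor's RT-CGM study reports −1.0% at 12 weeks with RT-CGM and −0.5% with SMBG, a between-arm difference of 1.0 − 0.5 = 0.5 percentage points. The first figures have no comparator value, come from a different study, and involve review of the patient's own trace rather than general glucose education. They make a contribution from components other than the display plausible but do not apportion it.

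**The case against.** The strongest reply is that the package is the intended intervention. The hypothesis and the central premise both say so, and randomisation supports a causal statement about the package. Learning to interpret RT-CGM readings is inherent in using it, and pattern review and the challenge are uses of CGM data. Contact also looks partly matched: controls have an instructor-led log review, and the compensation section implies four paid visits, (150 − 50)/25 = 4, with no difference by arm. All of this stands. It defeats any claim that the arm contrast is uninterpretable. It does not defend Aims 1 and 3 as worded, because general food/exercise-and-glucose education and a week 2 review of blinded data are separable from a real-time display.

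The mismatch over control content can also be read away. Section D's sequence includes monitoring with CGM, so its participants may be those in the intervention arm, and the Weeks 2, 6 text is explicit by arm. Study Procedures ties the glucose materials to the first use of RT-CGM, which points to the CGM arm. It is ambiguous rather than contradictory. What stands is that Section D, taken literally, does not match the visit-level text.

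A reader might infer several stronger points that the documents do not support:

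- *Goal-setting in general differs by arm.* It does not. The fat, calorie, activity and 7% goals go to everyone, and the request to controls for small changes belongs to their log review and does not replace the 7% goal. Only the glucose challenge is specific to one arm.
- *Most or all of the expected effect comes from components other than the display.* This would rest on single-arm HbA1c changes from different studies and would overlook the 0.5% fall under SMBG. HbA1c is also not the outcome named in Aim 1 or Aim 3.
- *Controls will be taught unevenly.* The protocol names one educator role, and nothing in it suggests inconsistent delivery.
- *The protocol claims to test the DPP material by itself.* Background says "This study would provide evidence that a modified DPP approach was effective when combined with RT-CGM". The qualifier about RT-CGM matters, and this is significance text, not an aim.

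**Conclusion.** The concern holds in a limited form. With the Weeks 2, 6 text as the operative description, the arms differ in the display and in three further components: glucose education, CGM pattern review and the glucose challenge. A between-arm difference would support the package and could not be credited to RT-CGM alone, so Aims 1 and 3 claim more than the hypothesis and the design allow. Section D and the Weeks 2, 6 text also need to agree on who receives the food-and-activity discussion of glucose.

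No numerical size can be given for the part not due to the display, and more participants would not supply one. The consequence is for what the trial may conclude. The conclusion assumes that the visit-level text governs; Appendices A and B are listed, but their content was not available to check how far the two sets of handouts overlap. It also presupposes an analysis that compares arms, which the SAP's time main effect in N=30 does not do.

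**What to change.** 1. Make Section D agree with the Weeks 2, 6 text so that one description states what controls receive, and name the arm for the glucose materials in Study Procedures.
2. Restate Aims 1 and 3, and the planned conclusion, as the effect of *RT-CGM plus glucose education and CGM pattern review, added to brief DPP counselling, versus brief DPP counselling alone*, with the challenge on averages counted as part of the pattern review.
3. As a precondition for either statement, have the SAP include the controls and target an arm contrast (arm by time in the mixed model).

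Items 1 and 2 are wording only. Their price is a slightly narrower claim, and item 3 changes the analysis text but not data collection.

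Giving the general glucose teaching to both arms, with a matching challenge for controls, is an optional design choice and not a required correction. It would bring the contrast nearer to the display and its interpretation, but it asks a different question and may shrink the arm difference. Rewording the Background sentence on the DPP approach is also optional.

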#### Study Procedures

**Medical Device/CGM/ DEXCOM G6**: CGM is a way to measure glucose levels in real-time throughout the day and night. A tiny electrode called a glucose sensor is inserted under the skin by a skin prick to measure glucose levels in tissue fluid. A small plastic piece of tube remains inserted in the skin. Typically you cannot feel this tubing once inserted. It is connected to a transmitter that sits on top of your skin and is about the size of a quarter. It is attached/secured by medical tape to your skin. It is approved for use on the abdomen for 10 days. It either records the sugars which we then download in our clinic (blinded part of the study) or it sends the information via wireless radio frequency to a monitoring/ display device or to a cellular phone so you can see your own data on your sugars. DEXCOM G6 is FDA approved for use in patients with diabetes and will be used in accordance with instructions as approved for diabetes. It is not currently an approved indication for patients with prediabetes, but will be used in accordance with instructions as approved for diabetes. The risk is minimal with this device use. In this study, we recommend patients connect this to their cell phones, but if not, we will provide transmitters for them for real-time monitoring. Study staff will insert the sensor, and then the patients pull off the sensor themselves after 10 days, and mail back to the study team.

Diabetes Prevention Program Educational Materials (see Appendix B): The DPP Group Lifestyle Balance™ (GLB) Program is a comprehensive lifestyle behavior change program adapted directly from the successful lifestyle intervention used in the National Institutes of Health funded Diabetes Prevention Program (DPP). The original individually administered DPP Lifestyle Balance intervention (copyright 1996; 2011) was developed and written at the University of Pittsburgh by the DPP Lifestyle Resource Core on behalf of the DPP Research Group and consolidated into 12 sessions designed to be administered weekly and potentially given by laypeople (32). Complete information about DPP is available at:

https://www.diabetesprevention.pitt.edu/index.php/for-the-public/for-health-providers/grouplifestyle-balance-curriculum. In this study, we will offer an adapted brief-intervention DPP in the first meeting. Our intent in providing this material is to support a primarily *self-directed* diet, activity and weight behavior modification context for use of the RT-CGM. Our diabetes educator will be responsible for reviewing the DPP materials and fat, calorie and activity goals at their original session along with materials developed about what different foods and activity does to your blood sugars prior to the initial use of RT-CGM. We reviewed the educational materials and handouts from the 12 sessions and consolidated them into a 12 page handout which was also reviewed by the current director of The Diabetes Prevention Support Center/DPP Lifestyle Resource Core at the University of Pittsburgh. Consistent with social cognitive theory, all participants are given fat and calorie goals based on their initial weight upon enrollment and an

Page 9 of 14

activity goal of 150 minutes of activity weekly with ongoing goal to 300 minutes weekly. They are asked to self–monitor weight, food intake and physical activity levels with goal of 7% weight loss (32).

**Measurements (Appendix C)**: We will measure HbA1c at the beginning of the study period and at 14 weeks. At each visit, blood pressure, weight, height, and waist circumference will be measured. At baseline and 14 weeks, questionnaires on diet and physical activity and selfperception questionnaires will be obtained. In the intervention group at 14 weeks, a questionnaire about CGM technology and perception of benefit of CGM use will be obtained, for diabetics and for prediabetics. Body composition will also be assessed serially by bioelectrical impedance using a Tanita scale at baseline and 6 weeks and 14 weeks. Pedometer data will be downloaded at 2 weeks, 6 weeks and 14 weeks. Physical fitness testing by resting heart rate and three minute stair step (amount of/change in steps climbed in 3 minutes) will also be obtained at baseline and 14 weeks.

**Anthropometrics: Height** will be recorded in centimeters and inches by a Stadiometer. **Weight** will be recorded in pounds and kilograms using a SECA Digital scale. **Waist circumference** will be meaured using a flexible measuring tape, and **blood pressure** taken with an Omron Professional Digital blood pressure machine.

**Bioelectrical impedance**: This will be collected with the Tanita Body Composition Machine. We will acquire body fat %, total body water %, fat free mass and more, in addition to BMI. To gather these measurements, subject's height and age are inputted into the machine, and subjects stand on the scale with bare feet. These values provide a better picture than simply weight and BMI of the overall subject's body composition.

**Food and Physical Activity Logs (Appendices M and N):** Participants in both groups will record their daily food intake and physical activity in these logs throughout the study. They will return these logs by mail for reviewing for 10 days after each study visit.

